9.6 Study size

The full PCBaSe database contains data on 185 729 men diagnosed with PCa since 1998 and more than 900 000 Pca-free men. This study will utilize the period from 2007 and contain approximately 98 000 men with PCa and about 500 000 men free of PCa from the population. More than 20% of patients with cancer will experience VTE (1). If the cumulative incidence within 5 years of follow-up is between 1% and 30%, the width of a 95% CI for the cumulative incidence of VTE will be approximately 0.12-0.58%. Although the corresponding cumulative estimate in PCa free men most likely is lower but on the other hand the sample size is larger, thus the resulting confidence interval is expected to be tight.

Table 1 shows the width of 95% CI for the cumulative incidence of VTE (based on binomial distribution) for different observed number of VTE among 98 000 patients.

Table 1. Estimated cumulative incidence (%) and two-sided 95% Binomial Confidence Intervals for 98 000 patients

Number of cases	Observed Cum Incidence (%)	Lower CI	Upper CI	Width (%)
980	1	0.94	1.06	0.12
1960	2	1.91	2.09	0.18
2940	3	2.89	3.11	0.22
3920	4	3.88	4.12	0.24
4900	5	4.86	5.14	0.28
9800	10	9.81	10.19	0.38
14700	15	14.78	15.23	0.45
19600	20	19.75	20.25	0.50
24500	25	24.73	25.27	0.54
29400	30	29.71	30.29	0.58

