9.2.3 Selection criteria from PCBaSe

PCa patients

Inclusion criteria

Initially all patients newly diagnosed with PCa between 2007-2016 with at least one year before the end of follow up date (31 December 2017) will be included.

From this population, a sub-population of PCa patients with a first cancer-related VTE event will be selected.

Exclusion criteria

No exclusions will be made.

Men without PCa

Inclusion criteria

All PCa-free men included in PCBaSe who are randomly selected from the general population of Sweden with the same birth year and county of residence of PCa patients diagnosed between 2007-2016.

Exclusion criteria

A PC free men diagnosed with a prostate cancer during the follow up will be identified and censored.

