9.4 Follow up

9.4.1 Exposure to anticoagulants

The exposure to AC treatment will be defined in two ways:

- the first is by following the patients until the end of the follow-up time, regardless if they are still on the drug or not.
- the second way is to follow up the patients until the filled prescription for each respective drug expires (“on/treatment”).

A grace period of 90 days will be used to define a new prescription of anticoagulant. The duration of a prescription will be derived from the median number of days between consecutive respective prescriptions after the grace period has passed.

The treatment exposure can then be used to study the switching of treatments and the discontinuation of treatments.

A start date will be defined as the date of the dispensed prescription for patients receiving anticoagulation.

Patients will be censored at earliest date of:

- Time of first occurrence of a recurrent VTE event or a bleeding event (major bleeding event i.e. intracranial, gastrointestinal, urogenital bleeding, or other bleeding leading to hospitalisation) or death
 - Patients will be followed until occurrence of one of the above mentioned outcomes of interest; similarly, the analysis is repeated in the same way for the other outcomes of interest. Therefore, the patients were not censored at the first outcome of interest and outcomes on treatment after the first is also taken in to account. Only first-time events of the same type are considered.
- End of observation time (data lock point for the database at 31st October 2017)
- Treatment discontinuation
- Treatment switching patients who switched will be censored at the time of the date of a filled prescription from a pharmacy of the new drug.

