9.8 Data analysis

Descriptive statistics will be used to define the socio-demographic and clinical characteristics (including main types of cancer therapies) of all PCa patients at the time of PCa diagnosis (Objective 1 and 3) and PCa-free men at the time of inclusion in PCBaSe (Objective 8) and include variables of interest listed above.

All categorical variables will presented by counts and proportions and continuous variables by mean, standard deviation, range, median, and first and third quartiles.

The occurrence will be estimated by calculating an incidence rate (accompanied by 95% CI) of cancer-related VTE events, split into PE and DVT events, in men with PCa (Objective 2) and in PCa-free men (Objective 10). The incidence rate is defined as the number of events of interest divided by the total number of person-years at risk. In men with PCa, the person-time at risk will be calculated from date of incident PCa diagnosis up until an outcome of interest, death or end of follow-up, whichever came first. The occurrence will be also described by Kaplan-Meier curves in different strata within different time-periods.

The AC treatment received by the PCa patients after a first cancer-related VTE event on an out-patient long-term basis will be reported by type of anticoagulation (LMWH, VKAs and NOACs) and its estimated duration (from the time-point of a hospital discharge up to 3 months, 3-6 months, more than 6 months) (Objective 4).

Time at risk for Objectives 5, 6 and 7 (recurrent VTE, bleeding leading to hospitalisation or death) will be calculated from first cancer-related VTE (the time-frame of defining cancer-relatedness will be specified later) for each events of interest up until event, death or end of follow-up.

The 95% CI for the incidence rate will be calculated using the Poisson distribution.

Incidence rates of recurrent VTE, bleedings and death will be calculated by the type and duration of AC treatment (stratification variables); however no comparative analysis of outcomes in three sub-groups of AC treatments, is planned.

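### Section 9.6 states the precision of a 5-year VTE incidence as if all 98 000 men were observed for 5 years; the exact widths are modestly too narrow

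*Protocol*

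**What the plan says.** The precision statement is in Protocol section 9.6. The cohort is described as follows: "This study will utilize the period from 2007 and contain approximately 98 000 men with PCa". The horizon and assumed range are given by "If the cumulative incidence within 5 years of follow-up is between 1% and 30" per cent, and the result is that "the width of a 95% CI for the cumulative incidence of VTE will be approximately 0.12-0.58" per cent. The table below that text is titled as giving "two-sided 95% Binomial Confidence Intervals for 98 000 patients", with rows from 980 cases (1%) to 29 400 cases (30%).

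Follow-up is fixed elsewhere:

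- Section 9.2.3 includes men "newly diagnosed with PCa between 2007-2016 with at least one year before the end of follow up date (31 December 2017").
- Section 9.4.1 gives another end of data: "End of observation time (data lock point for the database at 31st October 2017").
- Section 9.8 counts person-time from diagnosis "up until an outcome of interest, death or end of follow-up, whichever came first", and adds: "The occurrence will be also described by Kaplan-Meier curves in different strata within different time-periods".

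Section 9.6 makes no allowance for incomplete follow-up.

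**The concern.** A binomial interval with n = 98 000 is right for a 5-year risk only if the 5-year outcome of all 98 000 men is known. The protocol's own dates rule that out. A man diagnosed in 2016 contributes one to two years, and anyone diagnosed from 2013 on (from November 2012 with the October lock) falls short of five. With staggered entry, the variance of a Kaplan-Meier or cumulative-incidence estimate at 5 years depends on how many men are still under observation when events occur, and that number shrinks over time.

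This is the protocol's only numerical precision statement, and it bears on a primary objective, the occurrence of cancer-related VTE. What is at stake is whether the stated precision describes the planned cohort. Whether the study is large enough is not in doubt.

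**Working it through.** **Inputs from the protocol.** n = 98 000; 5-year cumulative incidence F from 1% to 30%; two-sided 95% (section 9.6). Diagnosis 2007-2016; end of data 31 December 2017 (section 9.2.3) or 31 October 2017 (section 9.4.1).

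**Assumptions, not in the protocol.** Diagnoses uniform over the ten years. VTE hazard constant, or with 50% or 80% of the 5-year cumulative hazard in year 1. Death ignored, or treated as censoring with 25% five-year mortality.

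**Step 1: reproduce the stated figures.** Width = 2 × 1.96 × √(F(1−F)/98 000).

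- F = 1%: 2 × 1.96 × √(0.01 × 0.99/98 000) = 0.125 points; limits 0.938-1.062, printed 0.94-1.06, printed width 0.12.
- F = 30%: 2 × 1.96 × √(0.30 × 0.70/98 000) = 0.574 points; limits 29.713-30.287, printed 29.71-30.29, printed width 0.58.

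The other rows reproduce in the same way, and exact (Clopper-Pearson) widths differ by no more than about 0.002. The printed widths are differences of rounded limits. The table is thus a complete-follow-up binomial.

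**Step 2: share of men with 5 years of potential follow-up.** Let E be the years from 1 January 2007 to the end of data: 11 (December) or 10.83 (October). The share still under potential observation at u years after diagnosis is G(u) = min(1, (E − u)/10).

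- December: G(5) = 6/10 = 60%, or 58 800 men.
- October: G(5) = 5.83/10 = 58%, or about 57 200 men.

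**Step 3: width with staggered entry.** Greenwood variance at 5 years:

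Var = (1 − F)² × ∫₀⁵ λ(u) / [n S(u) G(u) D(u)] du

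Here λ is the VTE hazard, S the VTE-free proportion, and D the proportion not censored by death (D = 1 if death is ignored).

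At low incidence S is close to 1, and without deaths the squared widening factor is the hazard-weighted mean of 1/G, which can be checked by hand:

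- Constant hazard, December: [1 + 10 ln(10/6)]/5 = 1.222; square root 1.105.
- Constant hazard, October: [0.833 + 10 ln(10/5.833)]/5 = 1.245; square root 1.116.
- 80% of hazard in year 1, December: 0.8 × 1 + 0.2 × [10 ln(10/6)/4] = 1.055; square root 1.027.

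Full numerical integration gives (ranges span the two end dates; factors span 1% to 30% incidence as well):

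| Scenario | Width at 1% | Width at 30% | Factor |
|---|---|---|---|
| Complete follow-up (Step 1) | 0.125 | 0.574 | 1 |
| No deaths, constant hazard | 0.138-0.139 | 0.640-0.646 | 1.11-1.12 |
| No deaths, 50% of hazard in year 1 | 0.133-0.134 | 0.617-0.621 | 1.07-1.08 |
| No deaths, 80% of hazard in year 1 | 0.128 | 0.592-0.594 | 1.03 |
| 25% mortality as censoring, D(u) = 0.75^(u/5), constant hazard | 0.149-0.151 | 0.696-0.703 | 1.20-1.23 |

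**Step 4: a crude ceiling for administrative censoring.** Using only the men with 5 years of potential follow-up in a plain binomial gives factors of √(1/0.60) = 1.29 to √(1/0.583) = 1.31. The widths are then 0.161-0.163 at 1% and 0.741-0.751 at 30%.

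**The case against.** Much of the opposing case stands.

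- **The table is not miscalculated.** As a binomial interval it is correct, and the text hedges with the word approximately. The fault is the unstated premise of complete follow-up combined with a 5-year horizon.
- **Not every printed row is too narrow.** A reader might infer this, but the documents do not support it. Some printed widths are rounded up: 0.22 against 0.214 exact at 3%, and 0.28 against 0.273 at 5%. With 80% of the hazard in year 1 and no deaths, the corrected widths there are 0.220 and 0.281, which round to the printed values. With 90% in year 1 they are 0.217 and 0.277, below print. Nothing in the protocol excludes such timing. The statement is safe only for unrounded widths.
- **The larger figures depend on how death is handled.** The 20-23% applies if death is treated as censoring. If death is a competing event, a man who dies has a known outcome, and only administrative censoring widens the interval.
- **This is not the interval planned for the main estimate.** Section 9.8 estimates occurrence as an incidence rate with a Poisson interval, which needs no 5-year completeness. Kaplan-Meier is an additional description. It would be wrong to read the error as carrying over to the reported rate.
- **No design decision depends on it.** The cohort is a whole registry, with no hypothesis test and no comparison of treatments. A reader might infer that the study is too small; nothing here supports that.

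What remains is that section 9.6 attaches a number to a 5-year risk by a method that the protocol's own dates contradict. That is a statement made in the protocol, not a detail left to a later analysis plan.

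**Conclusion.** The point holds, and it is minor. The 0.12-0.58 range is the precision of a fully observed cohort. Loss of risk set before 5 years can only widen the exact interval, so the direction does not depend on the assumptions, but the size does. Under uniform accrual, administrative censoring alone adds about 3-12% across the VTE timings tabulated. With death as censoring at an assumed 25% five-year mortality, the addition reaches about 20-23%.

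Even the crude ceiling in the working stays below about 0.8 percentage points. The protocol's conclusion that the whole-cohort estimate will be precise is therefore unaffected. The choice between the two end dates moves the widths by only about 1%, although the contradiction needs resolving in its own right.

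**What to change.** 1. Reconcile the end of data in sections 9.2.3 and 9.4.1 (31 December or 31 October 2017), because the 5-year risk set depends on it.
2. Restate the widths in section 9.6 from the expected number at risk, using a Greenwood or cumulative-incidence variance under the actual 2007-2016 accrual. State the assumed mortality, whether death is censoring or a competing event, and the assumed timing of VTE.
3. If that is not wanted, label the table as a best case under complete 5-year follow-up.

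Relabelling the table as 1-year incidence is not a good shortcut: follow-up would be nearly complete, but the rows up to 30% were set as a 5-year range.

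The cost is a few lines in section 9.6 and slightly less favourable widths. Cohort, data and analysis stay as they are.

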9.7 Data management

Data will be extracted from PCBaSe by members of the PCBaSe team according to routine procedures by the database owners.

Internal Bayer data analyst will have access to the anonymized data via a secure remote server to carry out the analysis. No individual data will be exported from secured server and only outputs in the form of figures and tables will be exported from the server.

9.8 Data analysis

Descriptive statistics will be used to define the socio-demographic and clinical characteristics (including main types of cancer therapies) of all PCa patients at the time of PCa diagnosis (Objective 1 and 3) and PCa-free men at the time of inclusion in PCBaSe (Objective 8) and include variables of interest listed above.

All categorical variables will presented by counts and proportions and continuous variables by mean, standard deviation, range, median, and first and third quartiles.

The occurrence will be estimated by calculating an incidence rate (accompanied by 95% CI) of cancer-related VTE events, split into PE and DVT events, in men with PCa (Objective 2) and in PCa-free men (Objective 10). The incidence rate is defined as the number of events of interest divided by the total number of person-years at risk. In men with PCa, the person-time at risk will be calculated from date of incident PCa diagnosis up until an outcome of interest, death or end of follow-up, whichever came first. The occurrence will be also described by Kaplan-Meier curves in different strata within different time-periods.

The AC treatment received by the PCa patients after a first cancer-related VTE event on an out-patient long-term basis will be reported by type of anticoagulation (LMWH, VKAs and NOACs) and its estimated duration (from the time-point of a hospital discharge up to 3 months, 3-6 months, more than 6 months) (Objective 4).

Time at risk for Objectives 5, 6 and 7 (recurrent VTE, bleeding leading to hospitalisation or death) will be calculated from first cancer-related VTE (the time-frame of defining cancer-relatedness will be specified later) for each events of interest up until event, death or end of follow-up.

The 95% CI for the incidence rate will be calculated using the Poisson distribution.

Incidence rates of recurrent VTE, bleedings and death will be calculated by the type and duration of AC treatment (stratification variables); however no comparative analysis of outcomes in three sub-groups of AC treatments, is planned.

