9.3 Variables

Baseline is defined as:

- in men with PCa: a date of an incident PCa
- in PCa-free men: a date of selection of PCa-free men (who are alive) into the database corresponding to the date of diagnosis for the index case

Index date is defined as:

- in men with PCa:
 - a date of a first cancer-related VTE event that is a VTE event related to the diagnosis of PCa (to define the relatedness, different time-frames will be specified and applied);
- in PCa-free men:
 - a date of selection into the database for defining a first recorded VTE event.

9.3.1 Characteristics of PCa and (where possible) PCa-free men:

- Age at PCa diagnosis
- Age at VTE
- Charlson Comorbidity Index (CCI) based on discharge diagnosis (including variables included into CCI)
- Specific events at baseline (that occurred prior and at the baseline) define by ICD codes for:
 - intracranial bleeding
 - gastrointestinal bleeding
 - urogenital bleeding
 - ischaemic heart disease
 - myocardial infarction

- heart failure
- stroke (ischaemic and haemorrhagic)
- transient ischaemic attack
- atrial fibrillation
- renal impairment
- renal failure
- depression
- hypertension
- hyperlipidaemia
- diabetes
- asthma
- COPD
- other cancers than PCa
- previous VTE events
- Co-medications at baseline (120 before the index event) and during follow-up (from index date)
 - Antiplatelets
 - Proton pump inhibitors
 - NSAIDs
 - SSRIs
 - Oral steroids
 - Antibiotics
 - Lipid-lowering medications
- PCa/specific parameters:
 - County
 - Hospital type (university, non-university)
 - Clinical TNM staging
 - PSA (at time of PCa diagnosis)
 - PCa risk categories (defined at diagnosis according to a modification of the National Comprehensive Cancer Network Guideline):
 - a. Low-risk: T1-2, Gleason score of 2–6 and PSA < 10 n/ml
 - b. Intermediate-risk: T1-2, Gleason score 7 and/or PSA 10–20 ng/ml
 - c. High-risk: T3 and/or Gleason score 8–10 and/or PSA 20–50 ng/ml

- d. Regionally metastatic T4 and/or N1 and/or PSA 50–100 ng/ml
 - e. Distant Metastatic disease: or M1 and/or PSA > 100 ng/ml; however PSA cutoff to be discussed
- Anti-cancer therapies that are delivered by a filled out-patient prescription

9.3.2 For patients in the VTE sub-population:

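### Person-time for the cancer-related VTE rate does not stop when the relatedness window closes, so the Objective 2 rate is biased low by a factor that depends on the window

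*Protocol*

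**What the plan says.** **Numerator.** Objective 2 concerns cancer-related VTE in men with PCa. Section 9.3 defines this as a VTE related to the PCa diagnosis and adds: "to define the relatedness, different time-frames will be specified and applied". Section 9.8, when it turns to Objectives 5 to 7, again leaves the length open: "the time-frame of defining cancer-relatedness will be specified later".

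**Denominator.** Section 9.8 gives the general rule: "The incidence rate is defined as the number of events of interest divided by the total number of person-years at risk". For men with PCa it then says that "the person-time at risk will be calculated from date of incident PCa diagnosis up until an outcome of interest, death or end of follow-up", whichever is first. No stop at the close of the relatedness window is mentioned.

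**End of follow-up.** This is a calendar date. Section 9.2.3 gives 31 December 2017; section 9.4.1 gives a "data lock point for the database at 31st October 2017".

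**PCa-free men.** Their index date in section 9.3 is "a date of selection into the database for defining a first recorded VTE event". No relatedness window applies. Section 9.2.3 adds: "A PC free men diagnosed with a prostate cancer during the follow up will be identified and censored". Section 9.8 writes out a person-time rule for men with PCa only.

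**The concern.** A man is at risk of the counted event only while a VTE would be classed as cancer-related. Once the window has closed he cannot contribute an event, but under section 9.8 he keeps contributing person-years until death or the end of data. The resulting figure is not the rate inside the window, because the denominator is too long. It is not the rate over all follow-up either, because late events are left out. It depends heavily on the ratio of window length to follow-up length.

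Two things are at stake. Objective 2 is a primary objective, and because several time-frames are to be applied, the rates for different windows would differ partly for this mechanical reason. Also, the PCa-free rate uses any first recorded VTE after selection. A reader who puts the two rates next to each other would compare a windowed numerator over unwindowed time with an unwindowed numerator.

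**Working it through.** **The plan's own figure.** The protocol gives no expected rate or person-years. The only quantity to reproduce is the precision table in section 9.6 for 98 000 men. The Wald width is 2 × 1.96 × √(p(1−p)/98 000). At p = 0.01 this is 0.125%, and at p = 0.30 it is 0.574%, against 0.12% and 0.58% in the table. All ten rows agree within rounding of the limits. The table is sound, but it describes sampling error of a cumulative incidence and does not bear on bias in the rate.

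**Inputs from the protocol.** Diagnosis 2007-2016; end of data 31 December 2017 (section 9.2.3) or 31 October 2017 (section 9.4.1); person-time rule from section 9.8.

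**Assumptions, not in the protocol.** Diagnosis dates uniform over the ten years; constant mortality m from 0 to 10 per 100 person-years; window W of 0.5, 1, 2, 3 or 5 years after diagnosis, or unbounded.

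**Formula.** The numerator is the same under both denominators, so the understatement is a ratio of person-time. With F the time from diagnosis to end of data:

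factor = mean of (1 − e^(−mF))/m ÷ mean of (1 − e^(−m·min(F,W)))/m,

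which becomes mean F ÷ mean min(F,W) when m = 0.

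**By hand, no deaths, end 31 December 2017.** F is uniform from 1 to 11 years, with mean 6.0.
- W = 0.5: 6.0/0.5 = 12.0
- W = 1: 6.0/1.0 = 6.0
- W = 2: mean min(F,2) = 0.1 × 1.5 + 0.9 × 2 = 1.95; 6.0/1.95 = 3.08
- W = 5: mean min(F,5) = 0.4 × 3 + 0.6 × 5 = 4.2; 6.0/4.2 = 1.43

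**With 5 deaths per 100 person-years, same end date.** Total person-time is 20 × [1 − (e^(−0.05) − e^(−0.55))/0.5] = 5.03 years per man. Inside 6 months it is (1 − e^(−0.025))/0.05 = 0.494. The ratio is 10.2.

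| Window | m = 0, Dec 2017 | m = 5/100, Dec 2017 | m = 10/100, Dec 2017 | Range, either end date |
|---|---|---|---|---|
| 6 months | 12.0 | 10.2 | 8.8 | 8.6-12.0 |
| 1 year | 6.0 | 5.2 | 4.5 | 4.4-6.0 |
| 2 years | 3.1 | 2.7 | 2.4 | 2.4-3.1 |
| 3 years | 2.1 | 1.9 | 1.8 | 1.7-2.1 |
| 5 years | 1.43 | 1.34 | 1.27 | 1.26-1.43 |
| Unbounded | 1.0 | 1.0 | 1.0 | 1.0 |

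Moving the end of data to October 2017 lowers each factor for a bounded window by about 1-3%.

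**Cross-check with VTE as an exit.** At m = 5/100 and VTE rates from 5 to 50 per 1000 person-years, the factor is 10.17 to 10.07 at 6 months and 1.33 to 1.29 at 5 years, so the VTE rate hardly matters.

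**Illustration.** Take an assumed true VTE rate of 5 per 1000 person-years in both cohorts and m = 5/100. The rule as written gives 0.49, 0.97, 1.85 and 3.75 per 1000 for windows of 6 months, 1, 2 and 5 years. Person-time matched to the window gives 5.0, and so would an unwindowed rate in PCa-free men.

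**The case against.** **The window is unknown.** This is the strongest point on the other side, and it stands as a limit on size. The protocol defers the length, and the only VTE horizon it mentions is the 5 years of section 9.6, where the factor is only about 1.3-1.4. A reader might infer that the rate is diluted several times over whatever is chosen, or that the rule is wrong for any finite window. Neither follows: a window as long as the longest follow-up, about 11 years, removes nothing.

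**The SAP may settle it.** The window length can properly be left to an SAP. The person-time rule has not been left open, however. Section 9.8 states it, and choosing a window later does not change it. Nor can the end of follow-up be read as the end of the window, since section 9.2.3 gives it as a calendar date.

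**Other estimates exist.** Section 9.8 also plans Kaplan-Meier curves in different time-periods. Read inside the window, these are not diluted. That is correct, but the curves are an addition; section 9.8 names the incidence rate as the estimate of occurrence.

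**No cohort comparison is planned.** Also correct. VTE in PCa-free men is a separate descriptive objective, and section 9.2.4 says only that the populations may be compared with their baseline characteristics in mind. A reader might infer that the two rates can never be set side by side; matching the definitions removes the difficulty.

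**Events before diagnosis.** A reader might also suspect that a window could reach back before diagnosis and count events without person-time. Nothing in the protocol says so. Risk time starts at diagnosis, and section 9.3.1 lists previous VTE as a baseline characteristic.

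**Conclusion.** The concern holds in a conditional form. Under section 9.8 as written, the numerator is restricted by a relatedness window and the denominator is not, so the Objective 2 rate is biased downward for any window shorter than a man's follow-up. The direction is certain for such windows; the size depends on a length that the protocol does not give. It runs from about 9-12 times at 6 months to 1.3-1.4 times at 5 years, and to no effect if all VTE after diagnosis count. These figures rest on uniform diagnosis dates and constant mortality of 0-10 per 100 person-years, both assumed. With about 98 000 men the confidence interval would give no hint of the bias. The mismatch with the PCa-free definition matters only where the two rates are read together, which the protocol permits but does not formally plan.

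**What to change.** In section 9.8, state that for each relatedness window person-time in men with PCa ends at the earliest of event, death, end of follow-up and end of that window.

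For any reading against PCa-free men, do one of two things: apply the same window to them, counted from their selection date, or report the rate of all first VTE after baseline in both cohorts.

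The cost is about two sentences in section 9.8 and one truncation step in the program. No new data are needed, and the window length itself can still be set later.

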Data analysis	
Among men with PCa:
 
Descriptive statistics will be used to define the socio-demographic and clinical characteristics of all PCa patients at the date of incident PCa diagnosis (baseline) as well as main types of cancer therapies.
 
The occurrence (incidence rate) of cancer-related VTE events, split into PE and DVT events will be also described by Kaplan-Meier curves in different strata.
 
The anticoagulation (AC) treatment received by the PCa patients after the first cancer-related VTE event at an out-patient long-term basis will be reported by type of anticoagulation (LMWH, VKAs and NOACs) and its estimated duration (up to 3 months, 3-6 months, more than 6 months). Among this sub-group of patients, the occurrence (incidence rates) of recurrent VTE and the time to recurrence, post-VTE bleeding leading to hospitalisation, and mortality will be calculated by the type and duration of AC treatment.
 
Among PCa-free men:
 
Descriptive statistics will be used to define the socio-demographic and clinical characteristics of PCa-free men at the time of inclusion in PCBaSe (baseline).
 
The occurrence of VTE events, split into PE and DVT events will be also described by Kaplan-Meier curves in different strata.

Milestones	The project is planned to begin in May 2019 and will end in April 2020.

5. Amendments

<None>

6. Milestones

Table 1: Milestones

Milestone	Planned date
Study start	May 2019
Submission of application form for approval from Research Ethics Board Uppsala	March 2019
Development of a study file containing the data	June 2019
Upload study file Research Platform	June 2019
Registration in the EU PAS register	April 2019
Study end	December 2019
Final report of study results	April 2020

7. Rationale and background

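### The planned Kaplan-Meier curves for VTE, if read as absolute risk with deaths censored, overstate the share of men who get a VTE; use cumulative incidence curves with death as a competing event

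*Protocol*

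**What the plan says.** The main measure of VTE occurrence is a person-year rate (protocol section 9.8): "The incidence rate is defined as the number of events of interest divided by the total number of person-years at risk". Curves are added to it: "The occurrence will be also described by Kaplan-Meier curves in different strata within different time-periods".

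The Data analysis row of the Abstract (section 4) plans the curves for both populations. For men with PCa it says: "The occurrence (incidence rate) of cancer-related VTE events, split into PE and DVT events will be also described by Kaplan-Meier curves in different strata". For PCa-free men: "The occurrence of VTE events, split into PE and DVT events will be also described by Kaplan-Meier curves in different strata". These serve Objectives 2 and 9 of the Abstract (section 9.8 labels the latter Objective 10).

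For men with PCa, section 9.8 runs time at risk "up until an outcome of interest, death or end of follow-up, whichever came first". Death thus ends follow-up on the same footing as the administrative end. For recurrent VTE, bleeding and death after a first VTE, the rule is similar: "for each events of interest up until event, death or end of follow-up".

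Section 9.6 expresses precision in terms of absolute risk over 5 years: "the width of a 95% CI for the cumulative incidence of VTE will be approximately 0.12-0.58" percent, with Table 1 taking cases divided by 98 000 men.

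The protocol does not mention competing risks or a competing-event estimator, and the limitations in section 9.10 do not raise the matter.

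**The concern.** Kaplan-Meier assumes that a censored man could still have the event later and has the same future risk as those still followed. A man who has died cannot have a VTE. If deaths are censored, one minus Kaplan-Meier answers a hypothetical question (VTE risk if nobody died) and lies above the real share of men with a VTE whenever mortality is not zero.

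A reader of these curves will take the height at 5 years as the proportion of men affected, which is the kind of quantity used in Table 1. Because the excess rises with mortality, it also differs between groups. Strata with different mortality, or PCa and PCa-free men if their mortality differs, would be shown with unequal upward shifts. Section 9.2.4 expressly envisages comparisons between the two populations.

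**Working it through.** **The plan's own figure.** The Table 1 widths follow from the Wald interval, width = 2 × 1.96 × √(p(1−p)/98 000).

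- p = 1%: 0.125 points (stated 0.12)
- p = 5%: 0.273 (stated 0.28)
- p = 30%: 0.574 (stated 0.58)

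The differences are rounding. Table 1 is sound, and the point does not rest on an error in it.

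**Inputs.** The horizon of 5 years is from section 9.6. The protocol gives neither a VTE rate nor a death rate for these men, so both are assumptions: constant VTE hazard λ = 0.01 per year, and constant death hazard μ = 0.03, 0.05 or 0.08 per year. These death hazards correspond to 5-year survival exp(−5μ) of 86%, 78% and 67% in men without VTE.

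**Formulas.**

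- One minus Kaplan-Meier with deaths censored: 1 − exp(−λt)
- Cumulative incidence with death competing: λ/(λ+μ) × [1 − exp(−(λ+μ)t)]

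**Results at t = 5 years.** The first quantity is 1 − exp(−0.05) = 4.88% in every row.

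| Death per 100 PY | Cumulative incidence | Excess (points) | Relative excess |
|---|---|---|---|
| 3 | (1/4)(1 − exp(−0.20)) = 4.53% | 0.35 | 8% |
| 5 | (1/6)(1 − exp(−0.30)) = 4.32% | 0.56 | 13% |
| 8 | (1/9)(1 − exp(−0.45)) = 4.03% | 0.85 | 21% |

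For scale, Table 1 gives a full CI width of 0.28 points at 5%. The middle row's excess is about twice that (0.56/0.28 = 2.0).

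**Sensitivity to mortality.** Fix one minus Kaplan-Meier at 5.00% at 5 years and set μ = −ln(S5)/5, where S5 is the assumed 5-year survival.

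| S5 | Cumulative incidence | Ratio |
|---|---|---|
| 95% | 4.88% | 1.03 |
| 90% | 4.75% | 1.05 |
| 80% | 4.49% | 1.11 |
| 50% | 3.62% | 1.38 |
| 30% | 2.92% | 1.71 |

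The relative excess hardly depends on the VTE level: at S5 = 80% the ratio is 1.12 when one minus Kaplan-Meier is 1%, and 1.11 when it is 30%.

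**Sensitivity to horizon.** With λ = 0.01 and μ = 0.05, the excess is about 2.5% at 1 year (0.995% vs 0.971%), 13% at 5 years and 27% at 10 years (9.5% vs 7.5%).

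**The case against.** The strongest reply is that the curves are supplementary. Occurrence is estimated by a person-year rate with a Poisson interval, and stopping person-time at death is correct for a rate. This stands: Objectives 2 and 9 have a main measure that this point does not touch, which limits its weight.

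Four stronger readings are tempting, and the documents do not support them.

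- **That the protocol states deaths are censored in the curves.** It does not. The time-at-risk wording defines person-years and is given only for men with PCa. The list in section 9.4.1 that opens "Patients will be censored at earliest date of" and mentions death concerns anticoagulant exposure. Censoring at death is the natural reading of Kaplan-Meier under these rules, but it is an inference.
- **That elderly or metastatic strata are affected as planned.** The strata are not named. Age and the distant metastatic category appear in section 9.3.1 only as characteristics.
- **That curves for recurrence, bleeding or mortality are also wrong.** No Kaplan-Meier curve is specified for these outcomes; section 9.8 plans rates for them.
- **That the overstatement is a quarter or more.** The 27% figure needs a 10-year horizon. With diagnoses in 2007-2016 and follow-up ending in 2017, only men diagnosed in 2007 can reach it.

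One may also say that section 9.6 uses cumulative incidence only to illustrate precision and does not name it as the analysis target. That is fair. Yet it is the only absolute-risk quantity in the protocol, and the curves are the output a reader would set beside it.

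A statistical analysis plan, not at hand, could choose another estimator. But the protocol itself names Kaplan-Meier, so the choice has not been left open.

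**Conclusion.** The point holds for the first-VTE curves in men with PCa and in PCa-free men. Read as absolute risk with deaths censored, they overstate the share of men with a VTE. At 5 years the excess is about 8% to 21% in relative terms (0.35 to 0.85 points on 4.88%), assuming constant hazards, VTE at 1 per 100 person-years and death at 3 to 8 per 100 person-years. If 5-year survival is 95% it is only about 3%; longer follow-up and any high-mortality stratum make it larger. The direction is certain whenever mortality is not zero, but the size rests on assumptions that the protocol cannot confirm. It should be fixed, but it does not undermine the primary rates.

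**What to change.** In section 9.8 and in both places in the Data analysis row of the Abstract, replace the Kaplan-Meier curves for first VTE (all VTE, PE, DVT) by Aalen-Johansen cumulative incidence curves with death as a competing event and 95% CIs, in both populations. State that the time-at-risk rule applies to PCa-free men too. If curves for time to recurrence or bleeding are produced later, use the same estimator. Leave the person-year rates and their Poisson intervals as planned.

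The cost is one changed procedure and a few sentences. No new data are needed, because section 9.5 lists the Cause of Death Registry among the linked sources.
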